The total number of nights subjects will be expected to stay at the CRC is approximately 2 for the non-Hispanic, Caucasian subjects and approximately 8 for the subjects of Japanese descent. The maximal total duration of study participation for a non-Hispanic, Caucasian subject is approximately 37 days and approximately 47 days for the subjects of Japanese descent, if the maximum screening period, treatment, washout, and follow-up visit durations are used.

Treatment Period:

- In Treatment Period 1, all study subjects (both Japanese and Caucasian) will receive maribavir as a single oral dose of 400 mg.
- In Treatment Periods 2 and 3, all subjects of Japanese descent will receive maribavir as a single oral dose of either 200 mg or 800 mg, depending upon randomization assignment.

Assessments

- Serial blood samples for PK analysis will be collected in each treatment period for the determination of maribavir and ██████ plasma concentrations at pre-dose and up to approximately 24 hours post dose. These blood samples will be collected according to the Schedules of Assessments (Table 1, Table 2, Table 3, Table 4, Table 5, and Table 6).
- Safety and tolerability will be determined through assessment of treatment-emergent adverse events (TEAEs) from the first dose to the post-treatment follow-up telephone call at 7 (±4) days after the last dose of IP, and vital signs, electrocardiogram (ECG), and clinical laboratory evaluations on Day 1 pre-dose and up to 24 hours post dose in each treatment period.

Follow-up

- A post-treatment follow-up telephone call will occur at 7 (±4) days after the last dose of IP for each subject. Subjects who experience AEs will be followed longer if needed, including an unscheduled clinic visit if appropriate, depending on the nature, severity, and seriousness of the AE.

Inclusion and exclusion criteria:

Inclusion Criteria:

1. An understanding, ability, and willingness to fully comply with study procedures and restrictions.
2. Ability to voluntarily provide written, signed, and dated (personally or via a legally-authorized representative) informed consent/assent as applicable to participate in the study.
3. Healthy subjects of Japanese descent must have been born in Japan and must not have lived outside of Japan for >10 years; both parents and all 4 grandparents must be of Japanese origin. Healthy, non-Hispanic, Caucasian subjects must have both parents and all 4 grandparents of non-Hispanic, Caucasian origin.

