- Safety and tolerability will be determined through assessment of TEAEs from the first dose to the post-treatment follow-up telephone call at 7 (± 4) days after the last dose of IP, and vital signs, ECG, and clinical laboratory evaluations on Day 1 pre-dose and up to 24 hours post dose in each treatment period.

Follow-up

- A post-treatment follow-up telephone call will occur at 7 (± 4) days after the last dose of IP for each subject. Subjects who experience AEs will be followed longer if needed, including an unscheduled clinic visit if appropriate, depending on the nature, severity, and seriousness of the AE.

[figure not shown]
Rationale for Study Design and Dose Selection

- Maribavir 400 mg BID is the clinical dose currently being evaluated in the ongoing pivotal Phase 3 studies; therefore, a single oral dose of 400 mg maribavir was selected for evaluating the primary objective of this study – to compare maribavir PK between Japanese and Caucasian subjects. Maribavir has demonstrated time-independent PK and a favorable safety profile in previous Phase 1 studies. Therefore, evaluating PK following repeated dosing, eg, 400 mg BID, is not necessary in this study. Although dose proportionality of PK for doses from 50 mg up to 900 mg was demonstrated in previous studies in Caucasian subjects, to explore the appropriate clinical dosage in Japanese subjects the lower and higher dosages were also selected to assess dose proportionality and to support the future Phase 3 clinical

development of maribavir in Japanese subjects. Therefore, the secondary objective of the study was to evaluate dose proportionality of maribavir PK in subjects of Japanese descent. The doses of 200, 400, and 800 mg were selected for evaluating dose proportionality as a more than two-fold differences in systemic exposure to maribavir is not expected in Japanese subjects as compared to Caucasian subjects. As the primary objective is to compare maribavir PK at 400 mg, the 400 mg dose is to be evaluated in Treatment Period 1 in both Japanese and Caucasian subjects to avoid treatment period effects on this comparison.

Figure 1 Study Design Flow Chart

This is an open-label study to evaluate the PK, safety, and tolerability of single doses of maribavir in healthy, adult subjects of Japanese descent and matched, healthy, adult, non-Hispanic, Caucasian subjects. These cohorts of healthy, non-Hispanic, Caucasian subjects and healthy Japanese subjects need not be dosed at the same time.

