5.2 Concomitant Treatment

Concomitant treatment refers to all treatment taken between the dates of the first dose of IP and the end of the follow-up period, inclusive. Concomitant treatment information must be recorded on the appropriate CRF page.

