8.8 Safety Analyses

The Safety Set will be used to summarize safety data. Safety will be assessed for the following evaluations:

- Number, severity, seriousness, and causality of TEAEs
- Changes in vital signs ECGs, and clinical laboratory results (hematology, chemistry, and urinalysis) from baseline to post-baseline time points. Baseline is defined as the last non-missing assessment prior to the first dose.

Safety data, including TEAEs, 12-lead ECGs, vital signs (systolic and diastolic blood pressure, pulse rate, respiratory rate), and clinical laboratory data (biochemistry, hematology, and urinalysis), will be summarized with the descriptive statistics. Potentially clinically important findings will also be summarized or listed. The potentially clinically important values will be defined in the SAP.

Quantitative safety data as well as the difference from baseline, if applicable, will be summarized by descriptive statistics. Frequency counts will be compiled for classification of qualitative safety data. Direct safety comparisons between the two cohorts (the subjects of Japanese descent and Non-Hispanic Caucasian subjects) will be presented from the maribavir 400 mg dosing data. All other safety data from the 200 mg and 800 mg in the subjects of Japanese descent will be summarized and listed.

For each safety variable, the last value collected before the first dose of investigational product in that treatment period will be used as baseline for all analyses of that safety variable in that treatment period.

An AE (classified by preferred term [PT]) that occurred during the study will be considered a TEAE if it had a start date on or after the first dose of investigational product or if it had a start date before the date of the first dose of investigational product, but increased in intensity on or after the date of the first dose of investigational product. An AE that occurred after the follow-up phone call will not be counted as a TEAE.

Adverse events will be coded using the agreed-upon version of Medical Dictionary for Regulatory Activities, Version 23.0. or later. The number of events, incidence, and percentage of TEAEs will be calculated overall, by system organ class, and by PT. Treatment emergent adverse events will be further summarized by severity and relationship to investigational product. Adverse events related to investigational product, AEs leading to withdrawal, SAEs, and deaths will be similarly summarized/listed.

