Appendix 2.2 Collection of Adverse Events

All AEs/SAEs are collected from the time the informed consent is signed until the defined follow-up period stated in Section 7.1.4. This includes events occurring during the screening phase of the study, regardless of whether or not IP is administered.

All AEs/SAEs must be followed to closure (the subject's health has returned to his/her baseline status or all variables have returned to baseline), regardless of whether the subject is still participating in the study. Closure indicates that an outcome is reached, stabilization achieved (the investigator does not expect any further improvement or worsening of the event), or the event is otherwise explained.

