#### **5.5 Concomitant Medications (Therapies) and Procedures**

Concomitant medications will be coded using the World Health Organization Drug Dictionary Global B3 dated September 2019.

Medications (therapies) and procedures taken during the study will be considered concomitant to the treatment(s) a subject has taken during the duration of the medications. Medications with start and stop dates and times during the wash-out period or the 7 days follow-up period after last single dose of IP will be considered concomitant to the prior treatment(s) subject received. Any medication/therapy and procedure with a start date and time after 7 days following the date and time of the last single dose of IP will be considered post-treatment medication/therapy and procedure and not be considered a concomitant medication/therapy and procedure.

Concomitant medication usage presented by therapeutic class (according to Anatomical Therapeutic Chemical classification) and PT will be summarized based on the number and proportion of subjects by cohort, treatment group and overall, based on the Safety Set. Multiple medication usage by a subject in the same category will be counted only once.

All concomitant therapies, procedures and medication will be listed for the Safety Set.

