### 7.1 Adverse Events

Adverse events will be coded using MedDRA Version 23.0 or newer.

An AE (classified by preferred term) that occurs during the study will be considered a TEAE if it has a start date on or after the first dose of investigational product or if it has a start date before the date of the first dose of investigational product, but increases in severity on or after the date of the first dose of investigational product. If more than 1 AE with the same preferred term is reported before the date of the first dose of investigational product, then the AE with the greatest severity will be used as the benchmark for comparison to the AEs occurring during the study under the preferred term. Adverse events during the study will be assigned to the treatment(s) a subject has taken at the onset of the event. An AE with start date and time during the wash-out period or the 7 days follow-up period after last single dose of IP will be assigned to the prior treatment subject received. An AE that occurs more than 7 days after the date of the last dose of investigational product will not be counted as a TEAE.

An overall summary of the number of subjects with TEAEs as well as the number of events will be presented, including the number and percentage of subjects with any TEAEs, serious TEAEs, TEAEs related to investigational product and TEAEs leading to discontinuation of investigational product.

The number and percentage of subjects reporting TEAEs, as well as the number of events, in each cohort, each treatment group, and overall will be tabulated by system organ class (SOC) and preferred term (PT); by SOC, preferred term (PT), and maximum severity. TEAEs considered related to investigational product will also be summarized by SOC and preferred term. If more than 1 AE occurs with the same preferred term for the same subject, then the subject will be counted only once for that preferred term using the most severe and most related occurrence for the summarization by severity and by relationship to investigational product. Presentation by SOC and PT will present SOC sorted alphabetically and PT within SOC by descending incidence.

TEAEs and related TEAEs will be summarized by preferred term by descending frequency. Serious TEAEs, TEAEs leading to discontinuation of investigational product and serious TEAEs leading to death, will be summarized by SOC, preferred term, cohort, and treatment group.

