#### **14. CHANGES TO ANALYSIS SPECIFIED IN PROTOCOL**

The following change is made to this statistical analysis:

- More clarification is added for the Safety Analysis Set.

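### SAP 7.1 stops counting TEAEs 7 days after the last dose, the protocol counts to the follow-up call (Days 3–11), and the change is undeclared; separately, the two 400 mg columns cover unequal time

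*SAP*

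**What the plan says.** **End of TEAE counting.** Protocol 8.8: "An AE that occurred after the follow-up phone call will not be counted as a TEAE". The synopsis gives the same span, "treatment-emergent adverse events (TEAEs) from the first dose to the post-treatment follow-up telephone call", and Section 3.1 repeats it. Each places the call at 7 (±4) days after the last dose. Protocol Appendix 2.2 sets collection to match: "All AEs/SAEs are collected from the time the informed consent is signed until the defined follow-up period" described in Section 7.1.4, which is that call. SAP 7.1 instead says: "An AE that occurs more than 7 days after the date of the last dose of investigational product will not be counted" as a TEAE.

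**Concomitant medication.** Protocol 5.2: "Concomitant treatment refers to all treatment taken between the dates of the first dose of IP and the end of the follow-up period, inclusive". SAP 5.5 says that medication taken within the washout or "the 7 days follow-up period after last single dose of IP will be considered concomitant" to the preceding treatment. Anything started more than 7 days after the last dose is reclassified as post-treatment.

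**Declared changes.** SAP 14 lists one: "More clarification is added for the Safety Analysis Set".

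**Which column an event goes to.** SAP 7.1 assigns an event in the washout, or in the 7 days after the last dose, to the preceding dose. Japanese subjects always take 400 mg in Period 1 and have two further doses; Caucasian subjects take 400 mg once. Protocol 8.8 presents direct safety comparisons of the cohorts from the 400 mg data. Neither document sets a common window or adjusts for time at risk, and SAP 5.6 summarises exposure in mg only.

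**The concern.** There are two separate matters.

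1. The protocol and the SAP define the end of the TEAE period differently. The same collected event can be a TEAE under one and not under the other, depending on the day the site telephones. It would then drop out of every SAP TEAE summary, including the serious and related ones. SAP 14 is where a reader would look for such a change, and it is not there. The concomitant-medication limit has the same defect.

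2. The 400 mg comparison sets a column that closes at the next dose beside one that stays open until follow-up. Evaluating ethnic differences in safety is a stated purpose of the study (protocol 2.1). A reader of the table is not told that the columns cover different lengths of time.

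**Working it through.** **Inputs**
- Call day after the last dose, c: 7 − 4 = 3 to 7 + 4 = 11 (protocol synopsis, 3.1, 7.1.4).
- Protocol window after the last dose: c days.
- SAP window after the last dose: min(c, 7) days, because routine collection ends at the call.
- Japanese 400 mg window: 72–73 h, from the Period 1 dose to the Period 2 dose (footnotes to the protocol schedules and SAP 16.1; note to Figure 1).
- Half-life: about 5–7 h (protocol 1.2.3).

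The documents state no figure for counting time, so there is none to reproduce.

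**Formulas.** Days not counted by the SAP = max(0, c − 7). Ratio of the Caucasian to the Japanese 400 mg window = min(c, 7) × 24/72 under the SAP, and c × 24/72 if counted to the call.

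| Call day c | Protocol window (days) | SAP window (days) | Days not counted | 400 mg ratio, SAP | 400 mg ratio, to the call |
|---|---|---|---|---|---|
| 3 | 3 | 3 | 0 | 1.00 | 1.00 |
| 5 | 5 | 5 | 0 | 1.67 | 1.67 |
| 7 | 7 | 7 | 0 | 2.33 | 2.33 |
| 8 | 8 | 7 | 1 | 2.33 | 2.67 |
| 9 | 9 | 7 | 2 | 2.33 | 3.00 |
| 10 | 10 | 7 | 3 | 2.33 | 3.33 |
| 11 | 11 | 7 | 4 | 2.33 | 3.67 |

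With 73 h in place of 72 h, the largest SAP ratio is 168/73 = 2.30.

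**Part 1.** For calls on Days 3–7 both rules count the same collected events. For calls on Days 8, 9, 10 and 11 the SAP leaves out 1, 2, 3 and 4 days, which is 1/8 = 12.5%, 2/9 = 22.2%, 3/10 = 30.0% and 4/11 = 36.4% of the protocol window. At the 7-day limit, 168/7 = 24 to 168/5 = 33.6 half-lives have passed, so most later onsets would be background events.

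**Part 2.** Under the SAP the two 400 mg columns cover equal time only if the Caucasian call is on Day 3. The Japanese 200 and 800 mg columns differ again. Each is open for about 3 days when given in Period 2 and min(c, 7) days when given in Period 3. With 1:1 order the mean is (3 + min(c, 7))/2, or 3 to 5 days, against 3 days for Japanese 400 mg.

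**An input to reconcile.** Protocol Table 1 and SAP Table 4 label the washout as Study Days 3–5. A dose 72–73 h after Day 1 falls on Day 4, so the label and the footnotes do not agree. The figures above use the stated 72–73 h.

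**The case against.** The case for leaving this alone has real force.

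- **Part 1 rarely matters.** It needs a late call and a late onset, in descriptive tables, many half-lives after a single dose. The event is still collected. A line in SAP 14 would settle it. All of this stands, and it is why the point is small.
- **Seven days may simply be the nominal follow-up.** The Caucasian maximum participation of 37 days fits 28 + 2 + 7, not 28 + 2 + 11 = 41. That may explain the SAP wording, but it does not declare a change. Nor are the totals decisive: with doses 72 h apart, the Japanese maximum of 47 days fits 28 + 8 + 11.
- **A fixed limit has advantages.** It does not depend on when the site calls, and it is defined for a subject who is never reached. Both points stand, so a rule that counts to the call needs a fallback.
- **Part 2 is a refinement.** The assignment rule is explicit, and vital signs, ECG and laboratory tests follow the same post-dose times in both 400 mg groups, so only AE counts are affected. Dysgeusia, the most common TEAE in Phase 1, usually starts within 1 hour of dosing (protocol 1.2.5). This stands.

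Three stronger readings are tempting, and the documents support none of them. First, a reader might infer that the SAP hides or loses late safety events. Collection runs to the follow-up contact, and Appendix 2.5 requires related SAEs to be reported whenever they are discovered. Only the TEAE tabulation is affected. Second, a reader might blame the 7-day limit for the unequal 400 mg columns. The limit narrows the gap (at most 2.3, against 3.7 if counted to the call). The cause is three periods against one, combined with the assignment rule. Third, a reader might conclude that the comparison is biased against one cohort. A longer Caucasian window can add events, but Caucasian subjects leave the unit on Day 2 and are next questioned at the call, while Japanese subjects stay in the unit. The net direction is not known.

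**Conclusion.** **Part 1 is wrong as written, with a small effect.** SAP 7.1 contradicts protocol 8.8, 3.1 and the synopsis, SAP 5.5 contradicts protocol 5.2, and SAP 14 declares neither. Results can differ only if the call is on Days 8–11 and onset is after Day 7, by at most 4 days per subject. This rests only on the documents' own windows. How many events it would touch depends on the actual call days and background AE rates, which the documents do not give.

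**Part 2 is a cheap improvement, not an error.** The 400 mg columns differ in counting time by a ratio of 1.0 to 2.3 under the SAP, and up to 3.7 if counted to the call, taking the stated 72–73 h between doses. The comparison is descriptive, with 12 subjects per cohort. The effect is likely to be small, to fall mainly on events after 72 h, and to be uncertain in direction.

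**What to change.** **1. One declared rule.** Either of these will do:
- In SAP 7.1, change both the counting sentence and the assignment sentence to run through the post-treatment follow-up call, or through 7 days after the last dose if the call is not completed. Both must change; otherwise a TEAE on Days 8–11 has no dose column. Align SAP 5.5 with protocol 5.2.
- Keep the fixed 7 days in SAP 7.1 and SAP 5.5 and declare both changes in SAP 14.

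The Last Value on Treatment definition can stay, because no safety measurement is scheduled after Day 2 of the last period.

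**2. A common window for the cohort comparison.** Add one set of TEAE and related-TEAE tables limited to onsets within 72 h of dosing, for Japanese 200, 400 and 800 mg and Caucasian 400 mg. About 72 h is the time that every column has, even with a Day 3 call. For an onset with no clock time, count the dosing date and the next 2 calendar dates, and assign an onset on a dosing date to that day's dose. Keep the full-window tables and footnote each column's window. Reconcile the Days 3–5 washout label with the stated 72–73 h.

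**Cost.** SAP wording and one extra table set, built from AE start dates and times that SAP 7.1 already uses. The downsides are:
- Counting to the call widens the full-window imbalance (Caucasian column up to 11 days), so the footnotes are needed.
- Late onsets appear only in the full-window tables and listings.
- Untimed onsets counted by date cover somewhat less than 72 h. For an assumed 08:00 dose, this is 16 + 24 + 24 = 64 h.
- Ascertainment still differs after Caucasian subjects leave on Day 2, and the tables should say so.

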6.2.2 Dosing

The non-Hispanic, Caucasian subjects will receive a single oral dose of 400 mg maribavir (2×200 mg maribavir tablets) on Day 1. The Japanese subjects will receive 3 doses of maribavir: on Day 1 of Treatment Period 1, they will receive a single oral dose of 400 mg of maribavir (2×200 mg maribavir tablets); on Day 1 of Treatment Period 2, they will be randomized to receive a single oral dose of either 200 mg (1×200 mg tablets) or 800 mg of maribavir (4×200 mg maribavir tablets); and on Day 1 of Treatment Period 3, they will receive a single oral dose of whichever dosage they did not receive on Day 1 of Treatment Period 2 (200 mg or 800 mg).

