### 3. STUDY DESIGN

#### 3.1 General Description

This is a Phase 1, open-label, randomized, crossover, partially fixed sequence, single-center study. A total of 24 subjects will be enrolled: 12 subjects of Japanese descent and 12 non-Hispanic, Caucasian subjects. Non-Hispanic, Caucasian subjects will be matched to Japanese subjects based on age ( $\pm 10$  years), sex, and body mass index (BMI) ( $\pm 15\%$ ).

[figure not shown]

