#### **Treatment Period:**

The non-Hispanic, Caucasian subjects will have one Treatment Period. The Japanese subjects will have Treatment Periods 1, 2, and 3.

- In Treatment Period 1, all study subjects (both Japanese and Caucasian) will receive maribavir as a single 400 mg oral dose.
- Depending upon the randomization assignment on Day 1 of treatment period 2, all subjects of Japanese descent will be dosed in a crossover fashion in Treatment Periods 2 and 3. They will receive a single oral dose of either 200 mg followed by 800 mg maribavir or a single oral dose of 800 mg followed by 200 mg maribavir.

The study design flow chart is presented in [Figure 1](#).

Figure 1 Study Design Flow Chart

\*Washout period of 72 to 73 hours after treatment on Day 1.

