### **3.2 Randomization**

Subjects of Japanese descent who meet all the inclusion criteria and none of the exclusion criteria will be randomized (1:1 ratio) to either maribavir 200 mg or 800 mg on Day 1 in treatment period 2. Subjects will then be dosed in a crossover fashion with a single dose of maribavir based on their randomization assignment on Day 1 in Treatment Periods 2, and 3. There is no stratification for this study.

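### SAP 7.1 narrows the protocol's AE-withdrawal category to stopping the drug, which a Caucasian subject cannot do after the single dose, so the 400 mg cohort comparison of this category is one-sided

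*SAP*

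**What the plan says.** Protocol 8.8 (Safety Analyses) states: "Adverse events related to investigational product, AEs leading to withdrawal, SAEs, and deaths will be similarly summarized/listed". It does not say whether withdrawal means leaving the study or stopping the drug.

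SAP 7.1 (Adverse Events) uses drug discontinuation only, both in the overall TEAE summary and in the detailed tables: "TEAEs leading to discontinuation of investigational product and serious TEAEs leading to death, will be summarized by SOC, preferred term, cohort, and treatment group". It has no row for TEAEs that led a subject to leave the study. An event that starts in a washout or in the 7-day follow-up "will be assigned to the prior treatment subject received".

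The cohorts differ in the number of doses. Protocol 6.2.2: "The non-Hispanic, Caucasian subjects will receive a single oral dose of 400 mg maribavir". SAP 3.1: "The non-Hispanic, Caucasian subjects will have one Treatment Period. The Japanese subjects will have Treatment Periods 1, 2, and 3". Under SAP 3.2, Japanese subjects "will be randomized (1:1 ratio) to either maribavir 200 mg or 800 mg on Day 1 in treatment period 2" and take the other dose in Period 3.

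SAP 5.1 treats leaving the study and stopping the drug as separate outcomes. It summarises the reasons for each by cohort and overall, and lists the subjects by reason. SAP 14 records one change from the protocol: "More clarification is added for the Safety Analysis Set".

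**The concern.** Protocol 8.8 bases the direct safety comparison of the two cohorts on the 400 mg data, and Protocol 2.1 says the study will inform bridging of safety data to Japanese patients. Within that comparison, this category can register an event on one side only.

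A Caucasian subject who takes the 400 mg dose and then leaves because of an AE has no drug left to stop, so SAP 7.1 does not count the case. A Japanese subject with the same AE after 400 mg who does not go on to Period 2 is counted under 400 mg. A reader who sees one or two Japanese events against none in Caucasians could take a product of the design for a difference in tolerability.

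A milder form of the problem runs across doses in the Japanese cohort. Every 400 mg dose is followed by another planned dose, but only about half of the 200 mg and 800 mg doses are.

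**Working it through.** The plan gives no figure on this point to reproduce. The check is a count from the design, followed by its consequences.

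**Inputs**
- Subjects (SAP 3.1): "A total of 24 subjects will be enrolled: 12 subjects of Japanese descent and 12 non-Hispanic, Caucasian subjects".
- Doses: one for each Caucasian subject and three for each Japanese subject (SAP 3.1, Protocol 6.2.2).
- Order: 400 mg first, then 200 and 800 mg in an order randomized 1:1 (SAP 3.2), so about 6 subjects take each of these doses in Period 2 and about 6 in Period 3.
- Attribution: events go to the preceding dose (SAP 7.1).
- Denominator: SAP 7.1 does not state one. I assume all subjects given that dose, from its use of the Safety Set.
- No dropout, and every dose fully taken.

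**Step 1. Doses with another planned dose to follow**

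| Cell | Dosed (n) | Further dose planned (m) |
|---|---|---|
| Caucasian 400 mg | 12 | 0 |
| Japanese 400 mg (Period 1) | 12 | 12 |
| Japanese 200 mg (about 6 in Period 2, 6 in Period 3) | 12 | about 6 |
| Japanese 800 mg (about 6 in Period 2, 6 in Period 3) | 12 | about 6 |
| Total | 48 | about 24 |

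**Step 2. Expected tabulated rate**

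Let p be the same true chance, after any dose, of an AE that would make a subject stop. The expected rate in the table is p × m/n:
- Caucasian 400 mg: p × 0/12 = 0
- Japanese 400 mg: p × 12/12 = p
- Japanese 200 mg and 800 mg: p × 6/12 = p/2 each

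With identical true tolerability, the table is expected to show p against 0 between cohorts at 400 mg. Within the Japanese cohort, 400 mg is expected to show twice the rate of 200 or 800 mg. The 200 against 800 mg comparison is balanced, at p/2 each.

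**Step 3. How often it would show**

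The documents give no rate for p, so 2%, 5% and 10% are assumptions. The chance of at least one tabulated event is 1 − (1 − p)^m:

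| Cell | p = 2% | p = 5% | p = 10% |
|---|---|---|---|
| Caucasian 400 mg (m = 0) | 0 | 0 | 0 |
| Japanese 400 mg (m = 12) | 21.5% | 46.0% | 71.8% |
| Japanese 200 or 800 mg, each (m = 6) | 11.4% | 26.5% | 46.9% |

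For example, 1 − 0.95^12 = 0.460 and 1 − 0.95^6 = 0.265. One event among 12 subjects moves a rate by 1/12 = 8.3 percentage points.

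**Step 4. With study discontinuation tabulated**

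All 12 subjects in each cohort become countable at 400 mg. If the chance of leaving were the same p in both cohorts, each would have the 21.5%, 46.0% and 71.8% of Step 3. The design does not guarantee equal chances, as discussed under the objection.

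**The case against.** **The SAP's reading is a fair one.** The protocol's term is ambiguous, and the protocol also uses withdrawal for the drug: Appendix 2.3 lists drug withdrawn as an action taken, and Protocol 4.5 makes stopping the drug the trigger for the early-withdrawal evaluations. This stands. A reader might infer that the SAP contradicts or replaces a defined protocol category. The documents support only that it settles on the narrower meaning without saying so.

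**The cases are not lost.** Protocol 8.8 accepts a listing, and SAP 5.1 summarises and lists study discontinuations by reason, with AE among the reasons in Protocol 4.5.1. For Caucasians, cohort and dose coincide. This stands and limits the impact. However, SAP 5.1 is not broken down by SOC or PT, nor by dose for Japanese subjects, so it does not correct what the SAP 7.1 table shows.

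**Study withdrawal is not symmetric either.** Caucasian subjects go home on Day 2 and have one telephone call left. After 400 mg, Japanese subjects still face two doses and about six more nights in the unit (about 8 against 2 in Protocol 3.1). This stands: the added row reduces the asymmetry but does not remove it, and it needs a note.

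**There may be no events.** Protocol 1.2.5 reports good tolerability in Phase 1 and no withdrawal from treatment for taste disturbance, the most common event. With no events, every cell is zero under either definition. No test or decision rule uses this table, and the other safety tables cover both cohorts. This too stands.

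**Conclusion.** The concern holds in a limited form. The Caucasian cell and the contributions from Period 3 doses are structurally zero. As a result, the 400 mg cohort comparison of this one category can only point towards worse Japanese tolerability (0 of 12 against 12 of 12 doses able to give the event), and the 200 and 800 mg rates are diluted by about half relative to 400 mg.

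Two stronger readings are tempting. One is that the comparisons as a whole are zero by construction. They are not: Japanese subjects can register events after 400 mg and after whichever dose falls in Period 2, and 200 against 800 mg stays balanced. The other is that drug discontinuation is impossible for Caucasians. It is impossible only once the dose is fully taken. The 400 mg dose is two tablets, and SAP 5.7 counts subjects who completed administration, so an interrupted dose remains a rare exception.

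The impact is modest and descriptive. The counts rest on no dropout, even sequences and fully taken doses. The event probabilities rest on assumed rates. The halving at 200 and 800 mg also assumes that the table divides by all dosed subjects.

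**What to change.** 1. In SAP 7.1, in the overall summary and the SOC/PT tables, add TEAEs leading to study discontinuation for both cohorts, assigned to the dose at onset.
2. If drug discontinuation is kept, show it for Japanese subjects only, with the number who had a further planned dose as denominator (12 at 400 mg and about 6 at each of 200 and 800 mg, less any dropouts). Leave it out of the 400 mg cohort comparison.
3. Footnote the study-discontinuation row to say that Japanese subjects have more of the study left to withdraw from.
4. State in SAP 14 how the protocol's term has been read and what was changed.

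The cost is SAP and table-shell wording. The termination page already records why a subject left (SAP 5.1), and the AE page records the action taken with the drug (Protocol Appendix 2.3). The CRF itself is not among the documents. If it has no field tying a study discontinuation to a particular event, the link would have to be made from the recorded reason, for at most a few subjects.
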